patients must be in New York Heart Association (NYHA) class II, III, or IV with a left ventricular ejection fraction (LVEF) of ≤40%. The inclusion and exclusion criteria are shown in Table 1. A total of 165 patients will be included over 6 month. In total, 11 hospitals (local investigators) in Belgium with an HF clinic employing at least one certified HF nurse will be participating in patient recruitment. Patients are not randomised and will all be participating in the smartphone digital support intervention.

A screening register will be kept including reasons why eligible patients that do not participate are disregarding inclusion. Patients refusing participation will also be asked to complete a quality of life (QOL)-questionnaire at 6 months and 12 months which will be answered online. A total of 165 patients (who do not want to participate) will be asked to answer this questionnaire.

So the app will be made available to 165 patients for home monitoring and another group of 165 patients without an application will be asked to answer quality of life questionnaires.

Patients who agree to use the application can continue to use it after the study, if they wish.

Inclusion criteria	Exclusion criteria
Diagnosed with HF – NYHA class II-IV	Acute coronary syndrome
LVEF ≤40%.	High urgent listed for heart transplantation
Hospitalisation due to decompensated HF at the moment of inclusion or up to 1 week prior to inclusion (i.e. discharged ≤1 week prior to inclusion).	Planned revascularisation, TAVI, MitraClip and/or CRT implantation within 3 months after inclusion
Owning a smartphone and able to use an application	Known alcohol or drug abuse
Written informed consent obtained	Terminal renal insufficiency with haemodialysis or peritoneal dialysis
	Impairment or unwillingness to use the digital support equipment (e.g. dementia, impaired self-determination, lacking ability to communicate)
	Existence of any non-cardiac disease reducing life expectancy to less than 1 year
	Age <18 years
	Participation in other treatment studies or remote patient management programmes

Table 1 – Inclusion and exclusion criteria. NYHA: New York Heart Association. LVEF: left ventricular ejection fraction. CRT: cardiac resynchronisation therapy. TAVI: transcatheter aortic valve implantation.

Digital support platform

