Interventions because of the trial

Personalised alarm cut-offs can be programmed by the caregiver team. There is no scheduled study contact on top of the usual care contacts. In case of application alarms being triggered, the patient will be called and the situation will be assessed. If needed, the problem will be discussed with a cardiologist. In emergency situations, the patient will be asked to present to the emergency department.

Monitoring of alarms will not be continuous and will only take place during working hours throughout the working week (Monday to Friday) and patients will be instructed to call their general practitioner, the hospital, or the emergency number in case of problems and not to wait until they are contacted.

End-of-trial assessment

At the end of the trial, the assessments listed in Table 2 will be performed. Cost-related data will be collected: healthcare resource use, hospitalisation time, tests, procedures, and health expenditure. Cost-effectiveness will be calculated using healthcare cost data and work productivity and impairment (WPAI) questionnaire to calculate incremental cost-effectiveness ratio (ICER).

Re-evaluation at 12 months

After the end of the inclusion at 6 months, a re-evaluation of outcome parameters will take place at month 12 to evaluate the continued effect of the intervention after cessation.

	Baseline	Final visit month 6
Informed consent and patient information	X	
Medical history: past medical history, symptom control, NYHA classification, smoking behaviour, current medication	X	X
Physical examination including weight, height, blood pressure, heart rate	X	X
Length of initial hospital stay	X	
Registration of medication	X	X
Echocardiography	X	X
12-lead ECG	X	X
Laboratory tests: haemoglobin, haematocrit, leukocytes, thrombocytes, sodium, potassium, creatinine, NT-proBNP	X	X
ePROs: KCCQ-12, EQ5D, HeartQoL, PHQ9, HLS-EU-Q16, EHFSB-9, SUTAQ, WPAI.	X	X
Registration of events: hospitalisation (with the length of stay), emergency department visit, death		X
Cost-evaluation		X

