Table 2 – intervention design. ECG: electrocardiogram. ePRO: electronic patient-reported outcome. NT-proBNP: N-terminal prohormone of brain natriuretic peptide. KCCQ-12: Kansas City Cardiomyopathy Questionnaire. EQ5D: EuroQol 5-dimension questionnaire. HeartQoL: Health-related quality of life questionnaire. PHQ9: patient health questionnaire-9. HLS-EU-Q16: European Health Literacy Survey Questionnaire. EHFSB-9: European Heart Failure Self-care Behaviour scale revised into a nine-item scale. SUTAQ: Service User Technology Acceptability Questionnaire. WPAI : work productivity and impairment.

Health economic analysis

The costs considered for the cost-effectiveness analysis are direct costs of the smartphone-based digital support intervention and the care utilisation recorded during the inclusion of the trial. The costs for the digital support intervention consist of costs for data management using the application, costs for devices that are provided in selected patients (blood pressure monitor, weighing scale), and personnel costs for inclusion and time spent on follow-up of alarms.

Information on care utilisation will be collected at the end of the trial. Former studies have demonstrated that hospitalisation costs are the key driver of HF-related costs (7,8). This study will thus focus on reduction in length of hospital stay and reduction in rehospitalisations after initial hospitalisation. The 30-day and 90-day rehospitalisation rates will be assessed. All hospital-related costs will be collected from the hospital billing and financial departments. A distinction will be made between scheduled and non-scheduled hospitalisations. Scheduled hospitalisations for elective procedures and scheduled visits with the cardiologist or general practitioner will not be included in the cost-evaluation.

Implementation cost and cost-effectiveness will be assessed in this trial following a pre-post economic model. A historical cohort of all patients hospitalised for HF on a cardiology ward in 2019 in all participating centres will be assessed for comparison. Hospital bills and hospital administrative data based on the international classification of disease (ICD)-codes will be collected. Propensity matching will be applied.

QOL and healthcare-related costs will be collected in selected patients refusing to participate in the smartphone intervention.

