Cost reduction between the intervention group, the historical cohort, and the participation refusals will be calculated. Costs and outcomes (utilities) will be compared by calculation of the incremental cost-effectiveness ratio (ICER) (ICER = $(\text{cost}_{\text{intervention group}} - \text{cost}_{\text{historical cohort}}) / (\text{effectiveness}_{\text{intervention group}} - \text{effectiveness}_{\text{historical cohort}})$). The incremental cost represents the difference in total average cost per patient between the intervention group and the historical cohort or the participation refusals. Effectiveness will be calculated by comparing QOL in the intervention group versus the participation refusals.

Study endpoints

The endpoints that will be assessed are summarized in Table 3. As specified before, the objectives of the study are to demonstrate positive implementation measures (e.g. feasibility) as well as to demonstrate cost-effectiveness. Secondary objectives include assessment of clinical impact, based on measurement of clinical endpoints as specified in Table 3. Implementation outcome variables will be assessed using a mixed-method design. Patient and caregiver parameters will be calculated (e.g. time spent using the application). Questionnaires will be used to assess patient variables. Semi-structured interviews in a selection of patients and caregivers will be performed to assess further outcome variables regarding implementation.

Implementation outcome variables	
Feasibility and patient acceptability	SUTAQ, semi-structured interviews.
Caregiver acceptability and burden of care	SUTAQ, semi-structured interviews, daily time spent by case nurses using the platform
Adoption and sustainability	Number and percentage of patients refusing inclusion, of patients continuing application usage after 6 months. Total time-percentage ratio of patients using the application throughout the trial.
Implementation cost	Cost-related data: healthcare resource use, hospital days, tests, procedures, health expenditure. Cost-effectiveness: healthcare cost data, WPAI questionnaire, ICER. Cost of hospital stay at inclusion.
Quality of life, literacy and patient self-care	KCCQ-12, EQ5D, HeartQoL, PHQ9, HLS-EU-Q16, EHFSB-9, SUTAQ.
Clinical outcome measurement	
Combined endpoint	Unplanned CV readmission and all-cause mortality

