Individual endpoints	Symptom control (NYHA, KCCQ-12), emergency department visits, length of hospital stay during the trial, unplanned CV readmission, all-cause mortality.

Table 3 - Study endpoints. CV: cardiovascular. SUTAQ: Service User Technology Acceptability Questionnaire. KCCQ-12: Kansas City Cardiomyopathy Questionnaire. EQ5D: EuroQol 5-dimension questionnaire. HeartQoL: Health-related quality of life questionnaire. PHQ9: patient health questionnaire-9. HLS-EU-Q16: European Health Literacy Survey Questionnaire. EHFSB-9: European Heart Failure Self-care Behaviour scale revised into a nine-item scale. SUTAQ: Service User Technology Acceptability Questionnaire. WPAI : work productivity and impairment. ICER: incremental cost-effectiveness ratio.

Statistical analysis

Sample size

A total of 165 patients will be included in the study. The sample size is based on comparable implementation trials (9,10). An additional patient group will be included that is not part of the study intervention but will complete questionnaires; this is a non-randomized control group. A minimum of 165 patients will take part in this control group for completion of the study.

Statistical analysis

The primary analyses will be paired Student *t*-tests and Wilcoxon signed-rank tests comparing baseline, 6-month and 12-month values for all patient-level outcomes. Secondary analyses aimed at determining the longitudinal impact of the smartphone digital support programme (i.e., using outcome data from the additional time points), and the correlation of independent variables (e.g., patient characteristics and adherence rates) with outcomes will be analysed using general linear mixed-model procedures. In addition, descriptive statistics will be produced for all variables collected, and subgroup analyses will be performed. All statistical analyses will be performed using the statistical software application SPSS (IBM Corporation, USA).

Descriptive statistics will be produced for the indicators of the implementation outcome to provide an objective measure of implementation success.

Discussion

The Bedicare-HF study is the first study that will investigate implementation of a smartphone-based HF digital support system in a real-life context on the background of European GDPR and medical device regulations.

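### Paired before/after tests are fixed as the primary analysis for every patient-level outcome, but readmission, death, emergency visits and hospital days during the trial have no baseline value to pair with

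*Protocol*

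**What the plan says.** The statistical analysis section of the Protocol names paired t-tests and "Wilcoxon signed-rank tests comparing baseline, 6-month and 12-month values for all patient-level outcomes" as the primary analyses. A general linear mixed model is named as secondary, for longitudinal impact and for correlates of outcome. Descriptive statistics are promised in addition for every variable collected.

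Table 3 (Study endpoints) gives the combined clinical endpoint as "Unplanned CV readmission and all-cause mortality". Besides symptom control (NYHA, KCCQ-12), the individual clinical endpoints are "emergency department visits, length of hospital stay during the trial, unplanned CV readmission, all-cause mortality".

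Table 2 has columns for baseline and month 6. The row "Registration of events: hospitalisation (with the length of stay), emergency department visit, death" is marked under month 6 only. The length of the initial hospital stay is recorded at baseline as a separate item. The section on re-evaluation at 12 months refers to outcome parameters in general and does not list the events.

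Table 1 requires "Hospitalisation due to decompensated HF at the moment of inclusion or up to 1 week prior to inclusion".

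On rank, the study endpoints section states: "Secondary objectives include assessment of clinical impact, based on measurement of clinical endpoints as specified in Table 3".

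Two related items stand in the health economic analysis section: "The 30-day and 90-day rehospitalisation rates will be assessed", and "A historical cohort of all patients hospitalised for HF on a cardiology ward in 2019 in all participating centres will be assessed for comparison".

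**The concern.** A paired test needs the same quantity measured twice in the same patient. That holds for questionnaire scores, NYHA class and laboratory values. It does not hold for readmission, death, emergency visits or hospital days during the trial, which can only accrue after entry. Because the rule covers all patient-level outcomes, it takes in these endpoints as well.

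An analyst following the text would have to invent a baseline, and the choice of constant would then decide the direction and the significance of the result. The Objectives section includes demonstrating effectiveness, and the Discussion links a successful result to reimbursement in Belgium. A before/after p-value on hospitalisation or death could therefore be read as evidence about the app when it carries none.

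**Working it through.** **No figure of the plan to reproduce.** The sample of 165 is taken from comparable trials. The Protocol gives no alpha, power, effect size or event rate for it, and this point does not depend on how 165 was reached.

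**Inputs.** n = 165 (Protocol, Sample size). Assumed for illustration: two-sided alpha 0.05; true event rates of 5% and 10%; readmission of 30% and 90%.

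**Step 1: which endpoints have a baseline value?**

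| Endpoint in Table 3 | Baseline value of the same quantity? |
|---|---|
| NYHA, KCCQ-12 | Yes, measured at baseline and month 6 |
| Unplanned CV readmission | No; events registered at month 6 only |
| All-cause death | No; every patient is alive at entry |
| Combined endpoint | No; it inherits both problems |
| Emergency department visits | No; registered at month 6 only, not fixed by eligibility |
| Hospital days during the trial | No; the initial stay recorded at baseline is the qualifying admission, a different quantity |

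**Step 2: baseline set to 0 for everyone.** If k of n patients have an event, k differences equal +1 and the rest are 0.

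- Paired t: mean difference k/n, squared standard error k(n−k)/[n²(n−1)], so t = √[k(n−1)/(n−k)] with 164 degrees of freedom.
- Signed-rank, normal approximation with zeros dropped and ties corrected: z = √k.
- Signed-rank, exact: two-sided p = 2 × 0.5^k.

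| Events k | k/165 | t | p, paired t | p, signed-rank approx. | p, signed-rank exact |
|---|---|---|---|---|---|
| 3 | 1.8% | √(3×164/162) = 1.74 | 0.083 | 0.083 | 0.25 |
| 4 | 2.4% | √(4×164/161) = 2.02 | 0.045 | 0.046 | 0.125 |
| 5 | 3.0% | √(5×164/160) = 2.26 | 0.025 | 0.025 | 0.0625 |
| 6 | 3.6% | √(6×164/159) = 2.49 | 0.014 | 0.014 | 0.031 |
| 33 | 20% | √(33×164/132) = 6.40 | 1.5×10⁻⁹ | 9×10⁻⁹ | below 10⁻⁹ |

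Significance for worsening is reached at 4 events by the t-test or the approximate signed-rank test, and at 6 by the exact test. The binomial probability of at least 6 events among 165 is 0.84 at an assumed true rate of 5% and 0.999 at 10%. The test asks only whether some events occurred.

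**Step 3: index admission coded as 1 for everyone (readmission only).** Now the n−k patients without a readmission each contribute −1, so t = −√[(n−k)(n−1)/k].

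- k = 50 (about 30% readmitted): t = −√(115×164/50) = −19.4, p about 2×10⁻⁴⁴ for improvement.
- k = 148 (about 90% readmitted): t = −√(17×164/148) = −4.34, p about 2×10⁻⁵, still for improvement.

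The same 50 readmissions give p about 2×10⁻¹⁴ for worsening under the coding of Step 2. For readmission the sign depends only on the coding. For death the Step 3 coding is not available.

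**Step 4: do the other named methods cover these endpoints?** A general linear mixed model treats the outcome as a continuous repeated measurement; it is not an event, count or time-to-event method. Descriptive statistics cover the events but stand beside the paired tests and do not replace them. The 30- and 90-day rehospitalisation rates and the 2019 cohort sit in the economic analysis. The statistical section does not assign them to the combined clinical endpoint.

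**The case against.** The strongest reply is that clinical impact is a secondary objective, that the paired tests suit most of the listed outcomes, and that a statistical analysis plan could set event windows and methods. All of this is fair and limits the point. It does not remove it: the Protocol is not silent here but fixes a method for all patient-level outcomes, so a plan that treated events differently would contradict it.

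Some stronger readings are tempting but not supported:

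- A reader might infer that a paired test on hospitalisation must show improvement, because everyone enters on an admission. That requires counting the index stay as a baseline event. The endpoint is readmission, and nothing in the Protocol codes the index stay that way; a baseline of 0 gives the opposite sign. Nor does eligibility fix emergency visits.
- A reader might infer that nothing else is planned for events. Descriptive statistics for all variables and the 30- and 90-day rehospitalisation rates are planned. What is missing is their link to the combined endpoint.
- A reader might take 5 deaths (3%) as significant harm under the stated methods. That is so for the t-test (p = 0.025) but not for the exact signed-rank test (p = 0.0625).
- A reader might see the 2019 cohort as a ready comparator for a survival regression. It rests on hospital bills and ICD-coded administrative data, with no ejection-fraction limit stated, and capture of deaths after discharge or of readmissions elsewhere is not described.

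A look-back count before entry could supply a baseline for readmission and emergency visits. None is specified. For admissions it would lean towards improvement, because every patient enters on one, and it is impossible for death.

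**Conclusion.** The point stands in limited form. The stated primary analysis cannot give a valid result for unplanned cardiovascular readmission, all-cause death, their combination, emergency visits or hospital days during the trial. Applied literally to the event indicators, it either cannot be run or returns significance after 4 to 6 events in 165, in a direction set by the coding of baseline. The thresholds rest on n = 165 and an assumed two-sided 0.05; the probabilities of reaching them rest on assumed event rates. The absence of a usable baseline needs no assumption.

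The word primary in that section describes the type of analysis and not a primary clinical endpoint. The documents therefore do not support a conclusion that the implementation, cost or quality-of-life results fail for this reason.

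**What to change.** In the statistical analysis section of the Protocol:

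- Limit the paired tests and the linear mixed model to outcomes measured at baseline and follow-up, for example KCCQ-12, EQ5D, HeartQoL, PHQ9, NYHA and laboratory values.
- Report the combined endpoint as time from a stated origin (inclusion or index discharge) to first unplanned cardiovascular readmission or death, with cumulative event proportions and 95% confidence intervals at 30, 90 and 180 days.
- Report readmission and emergency visits with death taken into account.
- Record the date of each event at the month 6 registration.
- Draw no before/after effectiveness claim from event endpoints. State any comparison with the 2019 cohort explicitly, and limit it to outcomes captured in the same way in both groups.

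The cost is a wording change, event dates and slightly more analysis work, with no added visits or patients. The 30- and 90-day rates already require readmission dates. The price in inference is that the single-arm event results become descriptive. A comparison with the 2019 cohort is not a cheap addition, because its data sources would first have to be shown to match.

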The utility of smartphone applications for patient care is increasingly being appreciated and in Europe, clear guidelines exist for developers who aim to develop software as a medical device (6). The advantage of using smartphone applications is that little specialised equipment is needed and, if a digital support programme is proven successful, implementation can be widely performed at low cost.

In the current context of the Covid-19 pandemic, HF patients are particularly suffering from the difficulty to meet their cardiologist and HF nurse on a regular basis. Developing the possibility for remote monitoring is a key alternative to avoid re-hospitalization or severe clinical cardiovascular outcome.

We present the design of the Bedicare-HF trial, which aims to take digital support research a step further. It uses an implementation design approach in which a real-life setting will be approximated. The trial aims thus to not only demonstrate the effectiveness of a smartphone-based HF digital support approach but also the feasibility of implementation in a European healthcare context. Also, it aims to evaluate the cost-effectiveness of a smartphone-based digital support approach.

Objectives

The objectives of this study are to demonstrate feasibility, acceptability, adoption, sustainability, and safety of a smartphone-based digital support system in the healthcare system in Belgium and to demonstrate effectiveness, to evaluate the implementation cost of the system, and to demonstrate cost-effectiveness.

Methods

Study design

The study design is a multicentre implementation trial. The conduct of the study is guided by good clinical practice (GCP) in accordance with the Declaration of Helsinki and the laws and regulations applicable in Belgium. Written approval from the Ethics Committees at all involved centres is required and informed consent must be provided by each patient.

Patient recruitment

Eligible patients are consecutive patients that are hospitalised for HF decompensation. The patients will be included in the programme during their hospitalisation or up to one week after hospitalisation. All eligible patients will be offered to participate. At the time of inclusion,

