Another important strength of this trial is the emphasis on cost-evaluation and cost-effectiveness analysis which will provide useful information for possible reimbursement. By using semi-structured interviews the study aims to also evaluate important barriers for implementation in patients and physicians.

Conclusion

The Bedicare-HF study will investigate the implementation of a smartphone-supported HF telemonitoring and digital support intervention in a European legislative setting. The design is a multicentre implementation trial. It is an all-comers study in which information on participants but also on non-participants of the study will be collected. This design will allow to take the evaluation of HF digital support a step further and allows to evaluate a low-cost smartphone solution for HF telemonitoring and digital support in a real-life setting. The study will yield important information about the feasibility of implementation in a European healthcare context on a background of European medical device regulation for software. The results of this study will demonstrate if, and how, a smartphone-based digital support system improves the self-care capacities, clinical management, and health outcomes of patients with HF and will yield important information about the implementation of digital support systems into a specific healthcare setting. The results of our study are expected in 2022.

Ethical considerations and additional regulations

The study will be conducted in accordance with the study plan, Good Clinical Practice (GCP) guidelines, and the ethical principles for medical research involving human subjects, set out in the Declaration of the World Medical Association of Helsinki (the Helsinki Declaration). The present study will be submitted to the respective Ethics Committees of participating hospitals for approval. The study may only be started after approval by the respective Ethics Committees.

Any change in the study plan and/or in the study participant information and declaration of consent shall be submitted to the responsible Ethics Committees for approval. All such changes shall be approved by the Ethics Committees before implementation.

Funding

This is an investigator-initiated study sponsored by Comunicare Solutions SA and the Belgian Working Group of Heart Failure.

References

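### The protocol makes paired tests of every patient-level outcome primary, with no single outcome or contrast named, and so conflicts with its own ranking of the clinical endpoints as secondary

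*Protocol*

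**What the plan says.** Four parts of the protocol bear on rank.

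- **Statistical analysis.** The primary analyses are paired t-tests and signed-rank tests of baseline, "6-month and 12-month values for all patient-level outcomes". Mixed models for longitudinal impact and for correlates of outcome are secondary. Implementation indicators get descriptive statistics only.
- **Study endpoints, text.** "the objectives of the study are to demonstrate positive implementation measures (e.g. feasibility) as well as to demonstrate cost-effectiveness". It continues: "Secondary objectives include assessment of clinical impact, based on measurement of clinical endpoints as specified in Table 3".
- **Study endpoints, Table 3.** No entry is marked primary. The individual clinical endpoints are "Symptom control (NYHA, KCCQ-12), emergency department visits, length of hospital stay during the trial, unplanned CV readmission, all-cause mortality". KCCQ-12 also stands in the quality-of-life row, which belongs to the implementation block.
- **Objectives.** After the implementation aims, the study is "to demonstrate effectiveness, to evaluate the implementation cost of the system, and to demonstrate cost-effectiveness". The items in this list are not ranked.

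Table 2 schedules these instruments at baseline and month 6: "ePROs: KCCQ-12, EQ5D, HeartQoL, PHQ9, HLS-EU-Q16, EHFSB-9, SUTAQ, WPAI". It has no month-12 column, although the text plans a re-evaluation at 12 months.

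**The concern.** The plan states a rule here; this is not a detail left for a later document. A statistical analysis plan that followed the Statistical analysis section would treat every paired comparison as primary. NYHA and KCCQ-12 are patient-level outcomes, so they are primary under that section and secondary under Study endpoints. KCCQ-12 is also listed in both blocks of Table 3, so it serves the lead objective and the secondary one at once.

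The protocol intends to make claims from these data. Its Conclusion says the results will show whether the system "improves the self-care capacities, clinical management, and health outcomes of patients with HF", and its Discussion links success to reimbursement in Belgium. With no outcome singled out, any one scale that reaches significance at either follow-up could be reported as a primary result towards the effectiveness objective.

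**Working it through.** **Inputs from the protocol**
- Seven questionnaires in the quality-of-life row of Table 3: KCCQ-12, EQ5D, HeartQoL, PHQ9, HLS-EU-Q16, EHFSB-9, SUTAQ.
- Three time points, which give two contrasts with baseline (month 6 and month 12). Month 6 against month 12 would be a third, but it is not a change from baseline.
- n = 165. This figure rests on comparable trials and comes with no alpha, power, effect size or SD, so it cannot be reproduced.

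**Assumptions (not in the protocol)**
- Two-sided 0.05 per test, no adjustment, no true change.
- Equal correlation over time within each scale, so the two contrasts with baseline correlate 0.5.
- Equal correlation between scales, varied from 0 to 0.7.
- All 165 patients contribute all time points.

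**Step 1: uncorrelated scales.** For one scale, two z-statistics with correlation 0.5 give a chance of 0.0907 that at least one exceeds 1.96 in absolute value. The chance that at least one is significant in the favourable direction is 0.0454. Over seven scales:
- any false positive: 1 − (1 − 0.0907)^7 = 0.486
- falsely favourable: 1 − (1 − 0.0454)^7 = 0.278

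**Step 2: correlated scales.** Simulation of paired t-tests, n = 165, 10,000 runs per setting, seven scales and two contrasts with baseline:

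| Correlation between scales | Any false positive | Falsely favourable |
|---|---|---|
| 0 | 49% | 28% |
| 0.3 | 44% | 23% |
| 0.5 | 39% | 20% |
| 0.7 | 30% | 15% |
| Nominal, one test | 5% | 2.5% |

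Separate runs with fewer repetitions differ from these by about one percentage point.

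**Step 3: sensitivity to the count.** With WPAI added (eight instruments, two contrasts), any false positive is about 54%, 49%, 42% and 32% at the same four correlations. The falsely favourable figures are about 32%, 26%, 22% and 16%.

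**Step 4: after the fix.** One outcome and one contrast bring the error back to 5%. The standardised paired change detectable with 80% power is (1.960 + 0.842)/√165 = 0.22 with 165 complete pairs. If all 14 tests stayed primary under Bonferroni (0.05/14 = 0.0036 each), it would be 0.29.

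**The case against.** **The section may rank methods, not endpoints.** It speaks of primary analyses and sets paired tests against mixed models. That reading is possible, but nothing else in the protocol is named as primary, so it leaves the outcome unchosen.

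**A reader might infer three competing hierarchies.** The documents do not support that. The Objectives section is an unranked list, so there is one conflict, between Statistical analysis and Study endpoints.

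**The conflict is narrower than all outcomes.** Most of the counted questionnaires belong to the implementation block of Table 3, and testing those as primary does not contradict Study endpoints. Readmission, death, emergency visits and hospital days during the trial have no baseline value in Table 2 to pair with. The direct clash concerns NYHA and KCCQ-12. This stands. The wider fault, that no outcome or contrast is chosen, is separate and also stands.

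**A larger error rate is tempting.** Seven scales by three contrasts treated as independent give 1 − 0.95^21 = 66%. The three contrasts share the same measurements, so even with uncorrelated scales the figure is about 60%. One of the three is not a change from baseline, and only favourable results support an effectiveness claim. SUTAQ (acceptability) and HLS-EU-Q16 (literacy) would not ordinarily show clinical benefit either; leaving them out lowers the figures further.

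**Alpha and a multiplicity rule may sit in a statistical analysis plan not shown.** Their absence is therefore not the finding. An adjustment there could control error, but it would not say which outcome is primary or reconcile the two sections.

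**Bias is the larger threat.** Patients enter during, or within a week after, hospitalisation for decompensation, and there is no randomised control. Scores may improve without the application. This is correct, and the figures above, which assume no true change, do not address it.

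**Conclusion.** The point holds in a limited form. The protocol makes paired tests of all patient-level outcomes primary without choosing an outcome, time point or contrast, and this clashes with the secondary rank it gives to clinical endpoints that include NYHA and KCCQ-12.

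For seven questionnaires and two contrasts with baseline, the chance of any false positive is about 30% to 49%, and of a falsely favourable one about 15% to 28%. That is roughly 6 to 11 times the nominal 2.5% (15/2.5 = 6, 28/2.5 = 11). These sizes depend on the assumed per-test level, the number of scales and the correlations. The conflict between the sections depends on none of them. The protocol should be changed, and a change of wording is enough.

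**What to change.** - **Statistical analysis:** name one primary patient-level outcome and one contrast. KCCQ-12 from baseline to month 6 is an example, since Table 2 already collects it at both visits.
- **All other outcomes and contrasts:** label them secondary and report estimates with 95% confidence intervals.
- **Objectives and Study endpoints:** revise both so that the named outcome has the same rank throughout. If KCCQ-12 is chosen, this step is essential, because Table 3 lists it under the clinical endpoints now called secondary.

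No new data or visits are needed. The cost is an amendment, which under the protocol's own rules needs Ethics Committee approval, and the sponsor gives up primary claims on the other outcomes. The change controls chance findings only. It does not remove bias from an uncontrolled before-after comparison in patients enrolled around a decompensation, and the report should say so.
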